12.3.3 Reporting of medication errors, including overdose, abuse and misuse

Medication errors, including events of overdose, abuse or misuse must be reported on an AE form within 7 calendar days of obtaining the information. Reporting of overdoses must be based on actual IMP exposure. For overdose cases, the descriptive terms accidental or intentional overdose should be used. If an event is classified as an SAE, it must be reported as such.

12.3.4 Reporting of significant laboratory events

All laboratory reports must be reviewed by the investigator for significance.

Significant laboratory events present at screening should be recorded in the medical history section in the CRF. Significant laboratory events found at the following visits, and which meet the definition of an AE, must be recorded on an AE form.

A significant laboratory event should be recorded as an AE if one of the following is applicable:

- It is abnormal and clinically significant (medical judgement by investigator).
- It leads to a change or discontinuation of treatment.
- It fulfils a seriousness criterion.
- It indicates a potential safety risk to the subject.
- If Hy's law is fulfilled; AST and/or ALT ≥3 times upper normal limit and bilirubin ≥2 times upper normal limit and ALP is not >2 times upper normal limit

12.3.5 Reporting of pregnancies

The investigator must report information on pregnancy and pregnancy follow-up information including pregnancy complications, delivery and health of the infant until the age of one month within 14 calendar days of obtaining the information, using the pregnancy notification form and pregnancy follow-up form.

Complications in relation to pregnancy must be reported as AEs. In case of spontaneous abortion, any malformation of the foetus, foetal death, stillbirth or a congenital anomaly/birth defect/developmental delay, the event must be reported and followed up as an SAE.

Any abnormalities observed in a child (up to two years of age) and suspected to be related to intrauterine exposure to the IMP should be reported to ALK.

12.3.6 Reporting of SAE and pregnancies after end of trial

SAEs that in the opinion of the investigator are related to IMP that are brought to the attention of the investigator after the last follow-up phone contact must be reported immediately by using the contact details listed in this section.

All pregnancies occurring in trial subjects while exposed to IMP that are brought to the attention of the investigator after the last follow-up phone contact must be reported within 14 days by using the contact details listed in this section.

Clinical trial protocol	Date:	12-Nov-2021	
Trial ID: SU-G-01	Version:	4.0	
EudraCT No. 2020-000455-12	Status:	Final	
CONFIDENTIAL	Page:	53 of 77	

12.4 Safety surveillance

Safety surveillance will be performed by ALK at pre-specified intervals to evaluate safety data and perform ongoing evaluation of AEs, SAEs, and laboratory data.

12.5 DMC

A data monitoring committee (DMC) will not be established for this trial.

12.6 Pregnancy

Female subjects must be advised to notify the investigator immediately if they become pregnant. If a female subject becomes pregnant, she must discontinue IMP intake but may continue to be enrolled in the trial.

The investigator must report any pregnancy reported during the trial to ALK. Subjects will be informed that the investigator will report any pregnancy during the trial to ALK and that she will be asked to provide information about her pregnancy, delivery and health of her infant until the age of one month. If deemed relevant to collect information from the male partner, a separate informed consent has to be obtained.

13 EARLY TERMINATION OF TRIAL

ALK reserves the right to terminate the trial due to the following:

- Safety concerns
- Proven lack of efficacy from other completed trials with the same IMP

If the trial is prematurely terminated or suspended, the investigator should promptly inform the subjects and ensure appropriate therapy and follow-up. Furthermore, the investigator and/or ALK should promptly inform the pertinent IEC/IRBs and provide a detailed written explanation. The pertinent regulatory authorities should be informed according to national regulations.

Early trial termination may be the result of any single criterion specified below:

- IMP-related death of an individual
- IMP-related anaphylactic shock in at least 2 subjects defined as:

Acute onset of an illness (minutes to several hours) with involvement of the skin, mucosal tissue, or both (e.g. generalised hives, pruritus, or flushing, swollen lips, tongue, or uvula) AND medically confirmed reduced BP with associated symptoms of end-organ dysfunction (e.g. hypotonia [collapse], syncope, incontinence).

14 DATA HANDLING

The diary in the trial will be an eDiary. The site will be trained in the use of eDiary by sponsor representatives. The sites will then train the subjects in how to fill in the eDiary.

Clinical trial protocol	Date:	12-Nov-2021	ALK
Trial ID: SU-G-01	Version:	4.0	
EudraCT No. 2020-000455-12	Status:	Final	
CONFIDENTIAL	Page:	54 of 77	

An eCRF will be used for this trial. The data is entered by trained site investigator/staff into the eCRF according to guidelines. A completed eCRF is required for each subject who signs an informed consent. All eCRFs must be completed in English.

The completed eCRFs and eDiaries are the property of the sponsor and must not be made available in any form to third parties (except for authorised representatives of appropriate governmental health or regulatory authorities) without written permission of the sponsor.

14.1 eCRF

Data generated by the trial site and relevant for the trial will be recorded in the eCRF.

The sponsor or its representative will supply sites with access to the eCRF. The sponsor will make arrangements to train the site staff in the use of the eCRF. There will be no access to the eCRF without documented training in the system.

All eCRF data must be verified and approved by an investigator at the site.

The CRA will review the eCRF for completeness and accuracy and instruct the personnel at the trial site to make any required corrections or additions according to an eCRF completion guideline.

The information entered into the database is systematically checked and errors or omissions will result in queries, which will appear in the eCRF for resolution. Concomitant medications entered into the database will be coded using the World Health Organisation Drug Reference List (WHO Drug, September 1, 2019 or higher).

Medical history and AEs will be coded using Medical Dictionary for Regulatory Activities (MedDRA) (version 22.1 or higher).

14.2 eDiary

Starting at visit 3, an eDiary will be dispensed and data will be entered by the subject. The subject will be trained in the eDiary by the investigator or designee. In addition, a training video with information on the eDiary will be available for the subjects. The data will be reviewed by the investigator.

During the trial, data will be entered in an eDiary by the subject and transferred to the eDiary vendor database on a daily basis. If the subject has missed more than 2 days in a row the investigator/designee will be notified by email and must contact the subject. In addition, if the total compliance for a period is less than 80% the investigator/designee must contact the subject and retrain the subject in the use of the eDiary. The aim is for the overall compliance for a subject in the trial not to be below 80%.

There will be no other source documentation for these data other than the vendor database.

After database lock, all access to the eDiary will be set as "read only". The sponsor will extract blinded data from the eDiary system. The investigator will be provided with an electronic copy of the diary data collected at the specific site at the latest 3 months after end of trial, by the vendor. The eDiary data will be subject to periodic review by the sponsor. Findings during the review of the eDiary data will be evaluated by the investigator and updates/correction to the data can only be executed by the investigator or if raised by sponsor only executed after confirmation and approval by the investigator.

Documentation of the data load from the eDiary vendor to ALK will be described in the data management report.

Clinical trial protocol	Date:	12-Nov-2021	
Trial ID: SU-G-01	Version:	4.0	
EudraCT No. 2020-000455-12	Status:	Final	
CONFIDENTIAL	Page:	55 of 77	

14.3 Query handling

Query handling at the trial site will be performed according to the guidelines for the eCRF and eDiary systems. Queries are created by programmed validation checks according to an edit check specification. Queries will also be created based on manual data checks.

All data changes/query decisions are created with an audit trail capturing the old information, the new information, identification of the user making the correction, the date the correction was made, and the reason for change.

14.4 Laboratory data

Laboratory samples will be processed at a central laboratory selected by ALK. When the samples have been analysed and the data released, a laboratory report will be sent to the investigator. The investigator must review and sign the laboratory reports. The lab data are also imported automatically in the eCRF for investigator evaluation of outliers. At the end of the trial the blinded laboratory data will be provided electronically to data management at ALK.

The transfer of laboratory data to the eCRF will be described in a data transfer specification.

Documentation of receipt and quality check of laboratory and immunological data will be provided in a data management report.

14.5 Database lock

When the database has been declared to be complete and accurate by sponsor, the database will be locked and data will be unblinded. All accesses to the eCRF will be set as "read only". CRAs and non-sponsor staffs "read only" accesses will be revoked from the eCRF, when PDF files are received at site.

If changes to trial data become necessary after database lock this must be performed according to the current ALK Standard operating procedure (SOP).

A data archive for the site subject data files (eCRF, eDiary and Laboratory data) are produced and sent to the site.

The investigator must sign and date the data archive approval form and send it back to the sponsor.

Clinical trial protocol	Date:	12-Nov-2021	
Trial ID: SU-G-01	Version:	4.0	
EudraCT No. 2020-000455-12	Status:	Final	
CONFIDENTIAL	Page:	56 of 77	

15 STATISTICAL METHODS

Statistical analyses will be carried out by ALK. All computations will be performed using SAS[®] version 9.4 or later version.

All analyses requiring significance testing will be two-sided at a 5% significance level, unless otherwise specified. All confidence intervals will be two-sided 95% confidence intervals. In all analyses, the null hypothesis will be one of no difference between treatment groups and the alternative hypothesis will be one of a difference. Before database lock, a separate SAP detailing the specifications given below will be prepared and agreed upon. This includes a detailed description of the total analysis set, full analysis set (FAS), safety analysis set, the per protocol (PP) analysis set and asthma analysis set (analysis sets are defined in Section 15.3.

Numerical variables will be summarised in tables including mean, standard deviation, median, 25%-quantile, 75%-quantile, minimum and maximum.

Categorical variables will be summarised by tables displaying numbers and percentage of subjects in each category.

Any changes in the statistical methods compared to the final SAP will be documented in the ICTR. Post-hoc analyses, if any, will be clearly marked.

15.1 Estimands

A primary and secondary estimand is defined for each of the primary, key secondary and supportive secondary objectives (see Sections 2.4 - 2.6 and 15.1.2 - 15.1.4) and a discussion of intercurrent events relevant for their definition is given in Section 15.1.1. The main estimator and sensitivity estimators for each estimand are defined in Section 15.11.1. Approaches for handling intercurrent events and missing data are given in Section 15.11.2, 15.11.3 and 15.14.

15.1.1 Intercurrent events

Intercurrent events (IE) are events occurring after treatment initiation that affect either the interpretation or the existence of the measurements associated with the clinical question of interest. It is necessary to address IEs when describing the clinical question of interest in order to precisely define the treatment effect that is to be estimated.

The IEs that have been identified as relevant is discontinuation of trial treatment due to adverse event or lack of efficacy. Prior to unblinding, potential unforeseen IEs will be specified in SAP to make sure an unbiased definition of IEs.

Due to the long duration of allergy immunotherapy clinical trials, rescue medication is dispensed to every subject for ethical reasons. The use of rescue medication is, therefore, part of the treatment policy and as such, it is not classified as an intercurrent event for this trial.

If additional unforeseen and relevant IEs occur during trial conduct, they will be included in the specification and estimation of the trial estimands. The details of their inclusion and the strategies taken to address them for each estimand will be documented in the ICTR.

Clinical trial protocol	Date:	12-Nov-2021	
Trial ID: SU-G-01	Version:	4.0	
EudraCT No. 2020-000455-12	Status:	Final	
CONFIDENTIAL	Page:	57 of 77	

15.1.2 Primary estimand

Using the framework proposed in the ICH E9(R1) addendum (ICH 2020), the trial product estimand can be described by:

- A. Treatment: 5-grass mix SLIT-drops, where rescue medication is taken as required.
- B. Population: Subjects randomised in this trial will be adults ≥18 years of age, with a clinical history of allergic rhinoconjunctivitis (with or without asthma) as diagnosed by a physician and having had symptoms despite treatment with antihistamines or nasal steroids during the two previous grass pollen seasons
- C. Variable: Average total combined score (TCS) during the 2nd PGPS
- **D.** How to account for intercurrent events: under the hypothetical situation where all subjects had completed treatment for the planned duration (hypothetical strategy)
- E. Population summary: Absolute difference in means between treatment conditions.

A hypothetical strategy will be used to address the intercurrent event of discontinuation of trial treatment. As such, if a subject discontinues trial treatment, only diary data up until the time of discontinuation will be included in the analysis. Any diary data recorded after discontinuation of trial treatment will be excluded from the analysis. Details of the handling of IEs and missing data are provided in Section **15.11.2**.

15.1.3 Secondary estimand

Using the framework proposed in the ICH E9(R1) addendum (ICH 2020), the treatment policy estimand can be described by:

- A. Treatment: 5-grass mix SLIT-drops, where rescue medication is taken as required.
- B. Population: Subjects randomised in this trial will be adults ≥18 years of age, with a clinical history of allergic rhinoconjunctivitis (with or without asthma) as diagnosed by a physician and having had symptoms despite treatment with antihistamines or nasal steroids during the two previous grass pollen seasons
- C. **Variable**: Average total combined score (TCS) during the 2nd PGPS
- D. **How to account for intercurrent events:** regardless of whether subjects complete treatment for the planned duration (treatment policy strategy)
- E. Population summary: Absolute difference in means between treatment conditions

A treatment policy strategy will be used to address the intercurrent event of discontinuation of trial treatment. As such, if a subject discontinues trial treatment, all available diary data will be included in the analysis, regardless of adherence to treatment. Details of the handling of IEs and missing data are provided in Section **15.11.3**.

15.1.4 Estimands for key secondary and supportive secondary endpoints

The trial product estimand and treatment policy estimand, specified for the primary objective in Sections **15.1.2** and **15.1.3** respectively, are defined similarly for each of the key secondary and supportive secondary objectives, where the relevant key secondary and supportive secondary endpoints of interest is specified in attribute C.

Clinical trial protocol Trial ID: SU-G-01	Date: Version:	12-Nov-2021 4.0	
EudraCT No. 2020-000455-12	Status:	Final	
CONFIDENTIAL	Page:	58 of 77	

15.2 Sample size and power considerations

General considerations:

In this trial, primary and secondary endpoints are tested hierarchically to control the family-wise error rate at 5% level. Individual endpoint analyses are based on treatment comparisons using a 2-sided t-test on a 5% level of significance.

The power calculations were done in two steps. The initial sample size calculation was done for observed cases only. This sample size is then evaluated using the estimand framework. The power is calculated for both the primary endpoint (TCS) and the key secondary endpoint (RQLQ). It is expected that the treatment difference in RQLQ is greater than the minimal clinically important difference (MCID) (0.16).

TCS power calculation:

The estimated TCS mean, standard deviation and treatment differences during the peak season from three trials is presented in **Table 8**. The power calculation is based on a TCS treatment difference of 21% (1.64 in absolute value) and a common standard deviation of 5.5. Under these assumptions, the trial has a power of 80% with the sample size of 180 evaluable subjects. The power will be 86% for the primary estimand and 80% for the secondary estimand with the assumption that 10% out of 220 subjects will discontinue the trial, with 4.5% of subjects discontinuing due to adverse events and 1% due to lack of efficacy each year.

Table 8	Mean and standard deviation of TCS during the peak of a season.
---------	---

Trial	Placebo μ (σ)	Active μ (σ)	Difference Absolute (relative)
GT-08 2006	8.44 (5.48)	5.14 (4.06)	3.3 (39%)
P05238	7.74 (6.50)	6.10 (5.09)	1.64 (21%)
P08067	5.73 (5.03)	4.56 (4.60)	1.17 (20%)
Average			2.04

RQLQ power evaluation:

The estimated RQLQ mean, standard deviation and treatment differences during the peak season from 3 trials raw data is presented in **Table 9**.

Table 9Mean and standard deviation of RQLQ during the peak of a season.

Trial	Placebo	Active	Difference
	μ (σ)	μ (σ)	Absolute (relative)
GT-08 2005	1.82 (1.11)	1.37 (0.97)	0.45 (25%)

Clinical trial protocol	Date:	12-Nov-2021	ALK
Trial ID: SU-G-01	Version:	4.0	
EudraCT No. 2020-000455-12	Status:	Final	
CONFIDENTIAL	Page:	59 of 77	

GT-08 2006	1.48 (1.05)	1.05 (0.91)	0.43 (29%)
P05238	1.73 (1.34)	1.41 (1.12)	0.33 (18%)
P08067	1.32 (1.11)	1.18 (1.08)	0.15 (11%)
Average			0.34

A common standard deviation of 1.15 has been assumed in the power evaluation. An expected placebo mean is 1.60 and an expected treatment difference is 0.34. With 180 evaluable subjects per treatment arm, the power of 93% is reached for testing if RQLQ treatment difference is greater than proposed MCID of 0.16. The power will be 95% for the primary and 92% secondary estimands for the sample size of 220 subjects with the same discontinuation assumptions as for TCS.

Conclusion:

The suggested sample size is 180 evaluable subjects per treatment arm. 220 subjects should be randomised in each arm, assuming a 10% discontinuation of subjects per year, where 1% discontinued due to lack of efficacy and 4.5% due to adverse events. In such case, the trial will have a power of at least 80% in order to detect a statistically significant difference of at least 21% with common standard deviation no larger than 5.5 for primary endpoint in observed case scenario. The trial will have a power of 86% and 80% for primary endpoint for primary and secondary estimands respectively. The trial will have a power of at least 93% to detect treatment difference greater than 0.16 in RQLQ for observed case. Similarly, 95% and 92 % for the primary and secondary estimand respectively.

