15.11.2 Handling of intercurrent events and missing data for the trial product estimand

For the trial product estimand, diary data occurring after discontinuation of trial treatment will be excluded from the derivation of the primary endpoint (see Section **15.1.2**). Subjects for whom the primary endpoint is missing (because of either missing diary data or the exclusion of diary data due to discontinuation of trial treatment) will be included in the analysis through multiple imputation under the hypothetical situation where subjects continued to take trial treatment as planned. Multiple imputation for subjects missing the primary endpoint will be conducted as follows:

- For subjects that discontinue trial treatment due to lack of efficacy, multiple imputation of the
 missing endpoint will be from the placebo group. This assumes that had the subject continued
 to take trial treatment, they would have experienced similar efficacy to subjects in the placebo
 arm. Data is assumed to be missing not at random (MNAR).
- For subjects that discontinue trial treatment due to treatment-related AEs, multiple imputation
 of the missing endpoint will be from their own treatment group. This assumes that the level of
 efficacy that would have been experienced by the subject if they had continued to take trial
 treatment is unrelated to the occurrence of the AE and, if they had continued to take trial
 treatment, they would have experienced similar efficacy to subjects in their own treatment
 group. Data is assumed to be missing at random (MAR).
- For subjects that discontinue trial treatment due to any other non-treatment related reason, multiple imputation of the missing endpoint will be from their own treatment group. This assumes that the level of efficacy that would have been experienced by the subject had they continued to take trial treatment is not related to their discontinuation of trial treatment. Data is assumed to be MAR.

The sensitivity estimator for the trial product estimand will use the multiple imputation policy described above for the main estimator except that:

For subjects that discontinue trial treatment due to treatment-related AEs, multiple imputation
of the missing endpoint will be from the placebo group. This assumes subjects reporting
treatment-related AEs would have been experienced a level of efficacy similar to subjects in
the placebo group if they had continued to take trial treatment. Data is assumed to be MNAR.

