The power calculations were done in two steps. This sample size wasthen evaluated using the estimand framework. The power was calculated for both the primary endpoint (TCS) and the key secondary endpoint (RQLQ). It is expected that the treatment difference in overall RQLQ during peak season is greater than the MCID of 0.10 and during entire season greater than 0.22 (Blaiss et al. 2022).

TCS power calculation

The estimated TCS mean, standard deviation and treatment differences during the peak season from three trials is presented in Table 8. The power calculation is based on a TCS treatment difference of 21% (1.64 in absolute value) and a common standard deviation of 5.5. Under these assumptions, the trial has a power of 80% with the sample size of 180 evaluable subjects. The power is 86% for the primary estimand and 80% for the secondary estimand with the assumption that 10% out of 220 subjects will discontinue the trial, with 4.5% of subjects discontinuing due to AEs and 1% due to lack of efficacy each year.

Trial	Placebo $\mu(\sigma)$	Active $\mu(\sigma)$	Difference absolute (relative)
GT-08 2006	8.44 (5.48)	5.14 (4.06)	3.3 (39%)
P05238	7.74 (6.50)	6.10 (5.09)	1.64 (21%)
P08067	5.73 (5.03)	4.56 (4.60)	1.17 (20%)
Average			2.04

Table 8: Mean and standard deviation of TCS during the peak of a season.

RQLQ power evaluation

The estimated RQLQ mean, standard deviation and treatment differences during the peak season from 3 trials raw data is presented in Table 9 below.

Table 9: Mean and standard deviation of RQLQ during the peak of a season.

Trial	Placebo $\mu(\sigma)$	Active $\mu(\sigma)$	Difference Absolute (relative)
GT-08 2005	1.82 (1.11)	1.37 (0.97)	0.45 (25%)
GT-08 2006	1.48 (1.05)	1.05 (0.91)	0.43 (29%)
P05238	1.73 (1.34)	1.41 (1.12)	0.33 (18%)
P08067	1.73 (1.34)	1.18 (1.08)	0.15 (11%)
Average	0.34		

A common standard deviation of 1.15 has been assumed in the power evaluation. An expected placebo mean is 1.60 and an expected treatment difference is 0.34. With 180 evaluable

Statistical analysis plan
Trial ID: SU-G-01
EudraCT No.: 2020-000455-12
CONFIDENTIAL

subjects per treatment arm, the power of 98% is reached for testing if RQLQ treatment difference is greater than proposed MCID of 0.1. The power is 95% for the primary and 92% secondary estimands for the sample size of 220 subjects with the same discontinuation assumptions as for TCS.

Conclusion

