The suggested sample size is 180 evaluable subjects per treatment arm. 220 subjects should be randomised in each arm, assuming a 10% discontinuation of subjects per year, where 1% discontinued due to lack of efficacy and 4.5% due to AEs. In such case, the trial has a power of at least 80% in order to detect a statistically significant difference of at least 21% with common standard deviation no larger than 5.5 for primary endpoint in observed case scenario. The trial has a power of 86% and 80% for primary endpoint for primary and secondary estimands respectively. Similarly, 95% and 92 % power for RQLQ for the primary and secondary estimand 0.1 in RQLQ for observed case.

8 Demographics and baseline characteristics

Summaries for numerical variables tables will display the descriptive statistics such as: mean, SD, median, min and max.

Summaries for categorical variables frequency tables will display counts and percentages.

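### The 86% TCS power stated for the primary estimand is about 6 points too high if 10% discontinue per year and about 2 points too high if 10% is the total; the plan words it both ways

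*Protocol*

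**What the plan says.** Protocol 15.2 sizes the trial on a TCS difference of 1.64, a common SD of 5.5 and a two-sided t-test at 5%. This gives 80% power with 180 evaluable subjects per arm. It then moves to 220 randomised per arm and gives estimand-specific power: "The power will be 86% for the primary estimand and 80% for the secondary estimand". SAP section 7 carries the figures over ("The power is 86% for the primary estimand and 80% for the secondary estimand") and repeats them in its conclusion ("The trial has a power of 86% and 80% for primary endpoint for primary and secondary estimands respectively").

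The discontinuation assumption appears in two forms. The TCS paragraph says "10% out of 220 subjects will discontinue the trial", with 4.5% for adverse events and 1% for lack of efficacy each year. The conclusion of the same section says "220 subjects should be randomised in each arm, assuming a 10% discontinuation of subjects per year". SAP section 7 has both forms too.

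For RQLQ, Protocol 15.2 gives 93% for observed cases against an MCID of 0.16, and then: "The power will be 95% for the primary and 92% secondary estimands for the sample size of 220 subjects". SAP section 7 lowers the peak-season MCID to 0.1 and raises the observed-case power to 98%, but keeps the estimand figures: "greater than proposed MCID of 0.1. The power is 95% for the primary and 92% secondary estimands".

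For the primary estimand, Protocol 15.11.2 imputes subjects who stop for lack of efficacy from placebo. For those who stop for treatment-related AEs or other reasons, "multiple imputation of the missing endpoint will be from their own treatment group". Protocol 15.11.1 and SAP 9.5.2 specify random sampling with replacement, 1,000 imputations and Rubin pooling.

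**The concern.** Drawing a missing average at random from observed subjects of the same arm adds no information about the treatment difference. Power under the primary estimand should therefore stay near the observed-case level for the number actually observed. A rise from 80% to 86% needs an explanation, and neither document gives one. The two discontinuation wordings also leave the number observed unclear. At stake is the stated power of the confirmatory analysis, which shows a margin over 80% that these inputs do not give.

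**Working it through.** **Inputs.** Difference d = 1.64, SD s = 5.5, two-sided 5%, n = 220 randomised and 180 evaluable per arm (Protocol 15.2); imputation and pooling as in Protocol 15.11.1, 15.11.2 and SAP 9.5.2.

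**Observed cases.** Noncentral t power, standard error s × √(2/n):

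| Observed per arm | Power |
|---|---|
| 178 | 80.1% |
| 180 | 80.5% (plan: 80%) |
| 198 | 84.1% |
| 209 | 86.0% |
| 220 | 87.7% |

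The plan's 80% reproduces. Power of 86% needs about 209 observed per arm, that is, at most 11 of 220 missing.

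**Number missing per arm.**
- Total wording: 220 × 0.10 = 22, leaving 198.
- Per-year wording: 220 × 0.9 × 0.9 = 178, so 42 missing. This is close to 220 − 180 = 40.
- The two named reasons alone come to 4.5% + 1% = 5.5% each year, about 11% over two years. That already exceeds a 10% total.

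**Planned imputation.** With m missing per arm and k of them imputed from placebo in the active arm, the expected estimate is d × (1 − k/n). Within-imputation variance is about s²/n per arm. Between-imputation variance is (m/n)² × s²/m = m × s²/n². The pooled standard error is therefore about s × √[(2/n)(1 + m/n)].
- m = 40, k = 4 (lack of efficacy, about 1% × 2 years × 220): estimate 1.64 × 216/220 = 1.610; SE = 5.5 × √[(2/220) × 1.182] = 0.570; ratio 2.82; power ≈ Φ(2.82 − 1.96) ≈ 80.6%. Simulation of a two-sample comparison gives 80.5%.
- m = 42: simulated 80.2 to 80.4%.
- m = 22, k = 2: estimate 1.64 × 218/220 = 1.625; SE = 5.5 × √[(2/220) × 1.1] = 0.550; ratio 2.95; power ≈ 84.0%. Simulation gives 84.0%, or 83.5% with k = 4.
- Late stoppers keep a score if they have one diary entry in the period (Protocol 15.14). If 10% per year acts over only 18 to 22 months (assumption), 32 to 39 are missing and power is 81 to 82%.

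**A construction that comes close to both stated figures.** Count all 220 per arm as observed (SE = 5.5 × √(2/220) = 0.524) and only dilute the effect:
- 2% from placebo: 1.64 × 0.98 = 1.607, power 86.4% (stated 86%).
- 11% from placebo: 1.64 × 0.89 = 1.460, power 79.3% (stated 80%).

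This omits the factor (1 + m/n), that is, the imputation uncertainty.

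**RQLQ.** The stated observed-case values reproduce as the probability that the observed difference exceeds the MCID, with difference 0.34 and SD 1.15. At 180 per arm: Φ[0.18/(1.15 × √(2/180))] = 93.1% for MCID 0.16, and Φ[0.24/(1.15 × √(2/180))] = 97.6% for MCID 0.1. Under the primary-estimand imputation:

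| MCID | 40 missing | 22 missing | Stated |
|---|---|---|---|
| 0.16 (protocol) | 92.8% | 93.7 to 93.9% | 95% |
| 0.1 (SAP) | 97.5% | 98.0 to 98.1% | 95% |

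With all 220 per arm observed and no dilution, the 0.16 value is 95.0%.

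**The case against.** The strongest reply is that 86% is not an underivable number. On the TCS paragraph's literal wording, 198 per arm gives 84.1%, within 2 points of it, and the dilution construction comes close to both TCS figures from the plan's own inputs. This stands: a reader might infer that 86% has no basis in the inputs, and the documents do not support that. That the sponsor used this construction is itself an inference. It fits RQLQ less well, giving 94.3% and 90.3% against the stated 95% and 92%. If it was used, it explains the figure without justifying it, because Rubin pooling does not treat imputed subjects as observed.

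The 80% and 84% come from a two-sample comparison, while the plan specifies an MMRM with asthma status and a site or country term. Protocol 15.2 also treats 5.5 as an upper limit for the SD. A residual SD of about 5.1 (40 missing) or 5.3 (22 missing) would give 86%. The arm SDs in Protocol Table 8 pool to 4.82, 5.84 and 4.82, so such a value is not implausible. However, neither document says a lower SD was used, and the trial that supplies the 1.64 is the one with 5.84. The restated values are therefore conditional on SD 5.5.

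The term evaluable is not defined, so 180 does not prove the per-year reading. The closing words each year in the TCS sentence might also be meant to cover the 10%; that would remove the conflict but leave the larger, 6-point gap.

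Finally, no decision rule uses the 86%. The SAP is dated 27-Oct-2023, after the last visit (22-Sep-2023), with 445 subjects randomised. This limits the consequence but does not make the figure right.

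**Conclusion.** With difference 1.64, SD 5.5 and the planned imputation and pooling, the primary-estimand TCS power is about 80% on the per-year wording and about 84% on the total wording. The stated 86% is about 6 or about 2 points too high. The per-year wording fits the 180 evaluable and the reason-specific rates better. These values assume a two-sample comparison and, at the ends of the range, that all who discontinue lack a 2nd-peak score.

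Three further inferences are not supported:
- That the trial is too small. The sizing of 180 evaluable for 80% is correct, and primary-estimand power stays at about 80% or more.
- That the secondary-estimand TCS power of 80% is wrong. Scenarios run from about 74% to 83%, depending on the unstated share of treatment-related AEs, the diaries retained after discontinuation and the number missing.
- That the RQLQ power is overstated throughout. At MCID 0.16 the primary-estimand 95% is about 1 to 2 points high (about 93 to 94%). At the SAP's 0.1 the carried-over 95% is too low (about 97.5 to 98%). That is a separate failure to update, and all the RQLQ values rest on the inferred criterion that the observed difference exceeds the MCID.

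**What to change.** In Protocol 15.2 and SAP section 7:
1. State once whether 10% is per year or in total, and make the reason-specific rates and the 180 evaluable agree with it.
2. Restate the primary-estimand TCS power as about 80% (about 84% if 10% is a total). Alternatively, give a value simulated under the planned imputation, Rubin pooling and MMRM, with its assumptions, including any residual SD below 5.5.
3. Recompute the primary-estimand RQLQ power on the same basis. In SAP section 7, recompute both 95% and 92% at the MCID of 0.1 used there, and state the criterion.
4. Keep the secondary-estimand 80% only with its assumptions: share of treatment-related AEs, diaries retained and number missing.

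The cost is a text change and, if chosen, one simulation. The stated TCS power becomes less favourable; sample size, analysis and error control are unaffected.
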